5.2.3.1. Management of Dose-Limiting Toxicities or Other Urgent Situations

In all cases, investigators may employ any measures or concomitant medications (following discussion with the sponsor when feasible), necessary to optimally treat the subject.

5.2.3.2. Follow-Up of Dose-Limiting Toxicities

Any DLT should be followed until it resolves to baseline or appears to have stabilized for a minimum of 4 weeks. During follow-up, subjects should be seen as often as medically indicated to assure safety.

5.2.3.3. Procedures for Cohort Review and Dose Escalation

Regular telephone conferences will be scheduled by the sponsor with study investigators in order to review cohort-specific data and overall safety data, to agree on dose escalation, adjudicate individual high-grade AEs as potentially dose-limiting, and guide other major study decisions.

5.2.4. Criteria and Procedures for Dose Interruptions and Adjustments of Study Drug

Treatment with INCB053914, L-DAC, azacitidine, or ruxolitinib may be delayed up to 2 weeks (≤ 14 days) to allow for resolution of toxicity. The second induction or consolidation cycles of I-DAC may be delayed until subject has recovered from I-DAC-related toxicities. Subjects may resume treatment if no medical condition or other circumstance exists that, in the opinion of the investigator, would make the subject unsuitable for further participation in the study. The treating investigator should contact the sponsor to discuss the case of any subject whose treatment has been delayed for more than 14 days before restarting treatment with INCB053914, L-DAC, azacitidine, or ruxolitinib.

Because subjects may enter the study with extensive pretreatment and/or severe bone marrow infiltration by the primary disease, these dose reduction rules are provided as guidelines (see [Table 5](#)). Individual decisions regarding dose reduction should be made using clinical judgment and in consultation with the sponsor's medical monitor, taking into account relatedness of the AE to the study drug or SOC agents, and the subject's underlying condition. Adverse events that have a clear alternative explanation or transient (≤ 72 hours) abnormal laboratory values without associated clinically significant signs or symptoms may be exempt from dose-reduction rules. Hematologic events (eg, thrombocytopenia, anemia, neutropenia) occurring in Part 1 TGB precipitating dose interruptions during Cycle 1 of treatment will be evaluated as potential DLTs ([Table 4](#)) and managed as per the guidelines in Section 5.2.3. Hematologic AEs that precipitate dose interruptions should be monitored for recovery at least every 3 days, if feasible.

CONFIDENTIAL

CONFIDENTIAL

Table 5: Guidelines for Interruption and Restarting of Study Drug

CHEMISTRY		
Adverse Event	Trigger	Action Taken
ALT and/or AST elevation	Grade 1	
 Continue study drug: 
 –Monitor LFTs at least weekly until < Grade 1 or baseline. –Carefully examine subject's concomitant medications for any that may contribute to LFT elevations. Hold these concomitant medications or switch to an alternative; consult medical monitor if needed. –Subjects with persistent but stable low-grade elevations (eg, < 1.5 × ULN) may revert to the routine LFT evaluation schedule as noted in Section 6.
	Grade 2	
 Continue study drug: 
 –Take actions as noted for Grade 1 elevations until LFTs have resolved to ≤ Grade 1 or baseline. –Refer to Appendix S for PHL case evaluation. –If Grade 2 elevation lasts ≤ 14 days, no action required. –If Grade 2 elevation lasts > 14 days, interrupt drug, monitor LFTs at least weekly, AND: 
 ▪ If resolved within 14 days after interruption, resume study drug at the same dose, monitor LFTs at least weekly during the next month and according to Protocol schedule thereafter. ▪ If LFTs do not resolve to ≤ Grade 1 or baseline within 14 days after interruption lasts, discuss with medical monitor.
	Grade 3 or 4	
 Refer to Appendix S for PHL case evaluation Complete a coagulation panel on the subject. Interrupt study drug and monitor LFTs at least weekly until ≤ Grade 1 or baseline: 
 –If resolved within 14 days after interruption subject may resume study drug at next lower dose (or at 25% reduction [Part 2 or Part 4], rounded down to the nearest strength). –If LFTs do not resolve to ≤ Grade 1 or baseline within 14 days after interruption, discuss with medical monitor. Carefully examine subject's concomitant medications for any that may contribute to LFT elevations. Hold these concomitant medications or switch to an alternative; consult medical monitor if needed.
Total bilirubin elevation	> 2 × ULN	
 Refer to Appendix S for PHL case evaluation If > 3 × ULN, interrupt treatment.
ALT and/or AST > 3.0 × ULN AND total bilirubin > 2.0 × ULN (Hy's law)		
 Interrupt treatment Refer to Appendix S for PHL case evaluation

 • Monitor LFTs according to Protocol schedule or more frequently if clinically indicated. • If Grade 2 or Grade 3 AST or ALT elevations recur upon restart of study drug, follow guidelines above, and if eligible to restart, resume study drug at next lower dose (or at 25% reduction [Part 2 or Part 4], rounded down to the nearest strength). If Grade 4 elevation recurs upon restart of study drug, discontinue study drug. • In subjects with liver metastasis-related elevations at baseline, contact sponsor to discuss clinical management and possible dose reductions. • Actions taken with any of the SOC combination agents in response to LFT elevations should be in accordance with the respective agents prescribing information. 		

CONFIDENTIAL

CONFIDENTIAL

Table 5: Guidelines for Interruption and Restarting of Study Drug (Continued)

HEMATOLOGY			
Parameter	Subjects	Trigger	Action Taken
Platelet count ($\times 10^9/L$)	Part 1 TGB	≥ 25 to < 50 sustained for > 7 days OR w/associated bleeding	
 Hold until resolved to ≥ 50. Restart study drug at same dose and monitor.
		< 25	
 Hold until resolved to ≥ 50. If recovery to ≥ 50 in ≤ 7 days, restart study drug at same dose and monitor. If recovery to ≥ 50 in > 7 days, restart study drug at next lower dose and monitor.
	Part 2 TGB Expansion Cohorts	< 25	
 Hold until resolved to ≥ 25. If recovery to ≥ 25 in ≤ 7 days, restart study drug at same dose and monitor. If recovery to ≥ 25 in > 7 days, restart study drug at next lower dose and monitor.
	Part 1 TGA Part 2 TGA Expansion Cohorts	N/A	Thrombocytopenia should be managed as per institutional standard, relevant to the underlying disease. If there is a suspected causal relationship to INCB053914 in the setting of a decreasing platelet count, hold INCB053914 and discuss with the medical monitor.
	Part 3 All Cohorts Part 4 All Cohorts	$\geq 50\%$ decrease from baseline platelet count (Subjects with baseline platelet count < 75)	
 Evaluate underlying disease based on peripheral blood and bone marrow assessment as needed. Consider dose interruption if cytopenias are NOT due to underlying disease or treatment with standard-of-care agents. Restart study drug at next lower dose (or 25% reduction if in expansion cohort, rounded down to the nearest tablet strength); monitor as clinically indicated.
ANC ($\times 10^9/L$)	Part 1 TGB Part 2 TGB Expansion Cohorts	< 0.5	
 Hold until resolved to ≥ 0.5. If recovery to ≥ 0.5 in ≤ 7 days, restart study drug at same dose and monitor. If recovery to ≥ 0.5 in > 7 days, restart study drug at next lower dose and monitor.
	Part 1 TGA Part 2 TGA Expansion Cohorts	N/A	Neutropenia should be managed as per institutional standard, relevant to the underlying disease. If there is a suspected causal relationship to INCB053914 in the setting of a decreasing ANC, hold INCB053914 and discuss with the medical monitor.
	Part 3 All Cohorts Part 4 All Cohorts	$\geq 50\%$ decrease from baseline ANC (Subjects with baseline ANC < 1.0 only)	
 Evaluate underlying disease based on peripheral blood and bone marrow assessment as needed. Consider dose interruption if cytopenias are NOT due to underlying disease or treatment with standard-of-care agents. Restart study drug at next lower dose (or 25% reduction if in expansion cohort, rounded down to the nearest tablet strength); monitor as clinically indicated.

CONFIDENTIAL

CONFIDENTIAL

Table 5: Guidelines for Interruption and Restarting of Study Drug (Continued)

HEMATOLOGY			
Parameter	Subjects	Trigger	Action Taken
Hemoglobin (g/dL)	All treatment groups/cohorts	< 6.5	
 Hold until resolved to ≥ 6.5, restart at same dose, and monitor. If recovery to ≥ 6.5 does not occur within 14 days of dose interruption or is refractory to transfusion support, discontinue study drug treatment(s) and follow-up per Protocol.
OTHER TOXICITIES			
Adverse Event		Action Taken	
Any Grade 1 or Grade 2 toxicity.		Continue study drug treatment and treat the toxicity; monitor as clinically indicated.	
Any Grade 3 toxicity, if clinically significant and not manageable by supportive care.		
 Interrupt study drug up to 2 weeks (14 days), until toxicity resolves to \leq Grade 1 or to baseline. Resume study drug at same dose. If assessed as related to study drug, resume at next lower dose (or 25% reduction, whichever is the smaller increment, rounded down to the nearest pill strength); monitor as clinically indicated. 	
Any recurrent Grade 3 toxicity after 2 dose reductions.		Discontinue study drug and follow-up per Protocol. (Exceptions require approval of sponsor.)	
Any other Grade 4 toxicity.		Discontinue study drug and follow-up per Protocol.	

Note: Dose reductions in Part 2 or Part 4 will use the next lowest dose evaluated in Part 1 or combination regimen in Part 3, respectively.

Up to 2 dose reductions of cytarabine, azacitidine, and ruxolitinib may be made at the discretion of the investigator.

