5.1.3.2. Supply, Packaging, and Labeling

INCB053914 will be provided as 15 mg and 50 mg round, white to off-white tablets packaged in high-density polyethylene bottles. The 15 mg tablets will be smaller than the 50 mg tablets.

No preparation of INCB053914 is required.

CONFIDENTIAL

CONFIDENTIAL

All Incyte investigational product will be labeled with the following statement, "Caution: New Drug—Limited by the United States law to investigational use," or in accordance with local regulatory requirements as applicable.

All Incyte investigational product labels will be in the local language and will comply with the legal requirements of each country.

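### Table 5 and its own note give different reduced INCB053914 doses in the expansion cohorts for ALT/AST elevations (Parts 2 and 4) and for platelet and ANC decreases (Part 4)

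*Protocol*

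**What the plan says.** Protocol Section 5.2.4, Table 5, sets out when to interrupt, restart and reduce INCB053914. For the expansion cohorts it contains these instructions.

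- **Grade 3 or 4 ALT/AST, once resolved:** "subject may resume study drug at next lower dose (or at 25% reduction [Part 2 or Part 4], rounded down to the nearest strength". The same wording is used when Grade 2 or 3 elevations recur on restart: "resume study drug at next lower dose (or at 25% reduction [Part 2 or Part 4], rounded down to the nearest strength".
- **Platelets and ANC, Parts 3 and 4:** "Restart study drug at next lower dose (or 25% reduction if in expansion cohort, rounded down to the nearest tablet strength". These rows apply to subjects whose baseline count was already low (platelets below 75 or ANC below 1.0 × 10⁹/L).
- **Platelets and ANC, Part 2 TGB, slow recovery:** "restart study drug at next lower dose and monitor", with no percentage option.
- **Other Grade 3 toxicity related to study drug:** "resume at next lower dose (or 25% reduction, whichever is the smaller increment, rounded down to the nearest pill strength". No study part is named.
- **Note under the table:** "Dose reductions in Part 2 or Part 4 will use the next lowest dose evaluated in Part 1 or combination regimen in Part 3".

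The note has no exception for liver or hematologic events, and no text ranks the rows against the note. On supply, Section 5.1.3.2 says: "INCB053914 will be provided as 15 mg and 50 mg round, white to off-white tablets". The planned combination levels in Tables 1 to 3 are 50, 65, 80 and 100 mg BID, and the footnotes allow them to change. Section 5.2.4 introduces the reduction rules as guidelines, to be applied with judgment and in discussion with the medical monitor.

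**The concern.** The bracketed reference to Parts 2 and 4 in the ALT/AST entries, and the reference to expansion cohorts in the platelet and ANC rows, tie the 25% cut to the cohorts for which the note requires the next evaluated dose. A site reading the row and a site reading the note can reach different doses after the same event.

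The conflict includes hepatic events. Section 1.4.4 names ALT/AST elevation as the expected treatment-emergent event of INCB053914, two of the three DLTs reported in Section 1.4.2 were ALT elevations, and Section 9.4.4.5 makes these elevations an adverse event of special interest. Safety and tolerability are primary objectives in all parts.

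The two instructions also differ in kind. The note keeps a reduced subject on a dose that has been studied as a cohort. The 25% wording can lead to doses such as 75, 60 or 45 mg BID, which are neither planned levels in Tables 1 to 3 nor among the Part 1 starting doses in Section 1.4.2. In addition, Section 5.2.5 treats an event needing more than two reductions as grounds for stopping unless the medical monitor agrees otherwise, so the size of each step bears on how far a subject can be reduced.

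**Working it through.** The plan states no reduced dose to reproduce, so each written instruction was applied to each planned BID dose.

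**Inputs.** Planned levels 50, 65, 80 and 100 mg BID (Protocol Tables 1 to 3; the same BID doses were used in Part 1, plus 115 mg BID, per Section 1.4.2). Tablets of 15 mg and 50 mg (Section 5.1.3.2). Assumption: strengths may be combined, so achievable doses are 15, 30, 45, 50, 60, 65, 75, 80 mg and so on.

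**Rules.**
- Note: next lower level on the list.
- 25% wording: 0.75 × dose, rounded down to an achievable dose.
- Smaller-increment row: the smaller of the two steps.

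| From (mg BID) | Note | 25% wording | Smaller-increment row |
|---|---|---|---|
| 100 | 80 (cut 20.0%) | 0.75 × 100 = 75 (cut 25.0%) | step 20 vs 25, so 80 |
| 80 | 65 (cut 18.8%) | 0.75 × 80 = 60 (cut 25.0%) | step 15 vs 20, so 65 |
| 65 | 50 (cut 23.1%) | 0.75 × 65 = 48.75, so 45 (cut 30.8%) | step 15 vs 16.25, so 50 |
| 50 | no lower planned level | 0.75 × 50 = 37.5, so 30 (cut 40.0%) | no level to compare |

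The note and the 25% wording differ at every planned level, by 5 mg BID at 65, 80 and 100 mg. The smaller-increment row matches the note at those three levels.

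**Two successive reductions.** From 100 mg BID: 80 then 65 under the note; 75 then 50 (0.75 × 75 = 56.25) under the 25% wording. From 80: 65 then 50, against 60 then 45. From 65: 50 and then no planned level, against 45 then 30 (0.75 × 45 = 33.75).

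**Where the conflict applies.**

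| Toxicity | Part 2 | Part 4 |
|---|---|---|
| ALT/AST | row and note conflict | row and note conflict |
| Platelets, ANC | TGB row agrees with note; TGA managed by institutional standard | row and note conflict |
| Hemoglobin | restart at same dose | restart at same dose |
| Other related Grade 3 | same dose as note at 65, 80, 100 mg | same dose as note at 65, 80, 100 mg |

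**Two gaps beside the conflict.** The note gives no dose if nothing lower was evaluated, for instance if 65 mg BID is chosen for Part 4 and Dose Level -1 was never opened. Rounding to the nearest strength is not defined for a dose built from two tablet strengths.

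**The case against.** The rows do not prescribe 25% alone; they name the next lower dose and put the 25% cut in parentheses. One can read the row as offering two options, with the note defining what the next lower dose means for cohorts that have no escalation ladder of their own. That is tenable for the words up to the parenthesis. It does not remove the conflict, because the note is worded as mandatory for Parts 2 and 4 and so rules out the option that the rows reserve for those parts.

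It can also be said that the rules are only guidelines, that individual decisions involve the medical monitor, and that Section 8.7 provides for regular teleconferences with subject-by-subject updates during expansion. This stands as a limit on the effect. A reader might infer that sites will in fact dose subjects differently; the documents do not show that. They show only that the text permits it, and that the monitor would be working from the same table.

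The size is modest: 5 mg BID per first step at 65 to 100 mg. The 50 mg case matters only if that level is carried forward or reached by an earlier reduction.

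A reader might also infer that Table 5 holds three rules with three different doses, or that all hematologic reductions in Part 2 are affected. Neither is supported. The smaller-increment row gives the note's dose at 65, 80 and 100 mg BID, and in Part 2 the TGB rows agree with the note while TGA cytopenias follow institutional practice.

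**Conclusion.** The conflict is in the current text and is not a product of redaction or of the amendment log. It is confined to ALT/AST elevations in Parts 2 and 4 and to platelet and ANC decreases in Part 4. There, the note and the row give different doses at every planned level: 80 against 75, 65 against 60, and 50 against 45 mg BID from 100, 80 and 65 mg BID, and no planned level against 30 mg from 50 mg BID.

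These figures assume the planned dose levels, which may change, and tablets that may be combined. They also read the Part 1 doses across both treatment groups; at the cutoff in Section 1.4.2, TGB subjects had received only 50 and 100 mg BID, so a within-group reading of the note would give different steps for Part 2 TGB.

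It would go too far to conclude that MTD decisions or the exposure summaries are invalid. Escalation decisions rest on Cycle 1 events in Parts 1 and 3 (Section 5.2.3), and SAP Section 6.4.1 uses doses actually administered. What is affected is the consistency of reductions after the event of most interest, and the reading of the reduction counts in SAP Section 10.2.5, which could pool two schemes. The point is an internal inconsistency of small size, worth correcting because it bears on the dose given after liver toxicity.

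**What to change.** Reconcile the ALT/AST entries (Parts 2 and 4) and the platelet and ANC rows (Part 4) of Table 5 with the note, so that each toxicity carries one unambiguous reduction instruction. State what applies when no lower dose was evaluated, whether evaluated doses are counted within or across treatment groups, and how rounding works with two tablet strengths. Different toxicities may keep different rules; what is needed is that each row and the note agree. Which rule to use is for the clinical team. The cost is a wording correction to one table and its note at the next amendment, with no effect on sample size or analysis.

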5.2.5. Criteria for Permanent Discontinuation of Study Drug

The occurrence of unacceptable toxicity related to study drug treatment will require that the study drug be permanently discontinued. Unacceptable toxicity is defined as follows:

- Occurrence of an AE that is related to treatment with the study drug which, in the judgment of the investigator or the sponsor's medical monitor, compromises the subject's ability to continue study-specific procedures, or is considered to not be in the subject's best interest.
- An AE requiring more than 2 dose reductions, unless further dose reductions are approved by the medical monitor.
- Persistent AE requiring a delay of therapy for more than 2 weeks (14 days) unless a greater delay has been approved by the medical monitor.

CONFIDENTIAL

CONFIDENTIAL

5.2.6. Dose Increases

Intrasubject dose escalation will be permitted in Part 1 and Part 3 with sponsor preapproval in the following circumstances:

- The Protocol eligibility criteria are met at the time of escalation (hepatitis serology and pregnancy testing do not need to be repeated).
- The subject has received ≥ 4 cycles of study drug without drug-related toxicity \geq Grade 2.
- The next dose level(s) has been determined to be safe based on the MTD criteria.
- Subjects in the monotherapy groups must be willing to submit to the PK sampling and ECG schedule as in Cycle 1 of Table 8. Supplemental PK sampling at the escalated dose is optional for subjects in the SOC combination groups and should be considered only if the subject is continuing to receive the combination agent.
- In the opinion of the investigator, the subject does not have any concurrent condition or circumstance that would complicate the dose escalation or PK sampling or pose increased risk to the subject.

5.2.7. Withdrawal of Subjects From Study Treatment

5.2.7.1. Withdrawal Criteria

Subjects **must** be withdrawn from treatment for the following reasons:

- Disease progression or treatment failure has occurred, as assessed by the appropriate disease-specific assessment criteria. If, in the investigator's opinion, the subject is receiving clinical benefit despite meeting criteria for progressive disease, the subject may continue to receive treatment with sponsor approval.
- An AE defined as unacceptable toxicity occurs (see Section 5.2.5).
- The subject becomes pregnant.
- Consent is withdrawn.
- Further participation would be injurious to the subject's health or well-being, in the investigator's medical judgment.
- The study is terminated by the sponsor.
- The study is terminated by the local health authority, IRB, or IEC.

A subject **may** be discontinued from study treatment as follows:

- If, during the course of the study, a subject is found not to have met eligibility criteria, the medical monitor, in collaboration with the investigator, will determine whether the subject should be withdrawn from the study.
- If a subject is noncompliant with study procedures or study drug administration in the investigator's opinion, the sponsor should be consulted for instruction on handling the subject.

CONFIDENTIAL

CONFIDENTIAL

5.2.7.2. Withdrawal Procedures

In the event that the decision is made to permanently discontinue the study drug, the subject will be withdrawn from the study and the end-of-treatment (EOT) visit should be conducted.

Reasonable efforts should be made to have the subject return for a follow-up visit. These visits are described in Sections 6.3 and 6.4. The last date of the last dose of study drug and the reason for subject withdrawal will be recorded in the electronic case report form (eCRF).

If a subject is withdrawn from study treatment:

- The study monitor or sponsor must be notified.
- The reason(s) for withdrawal must be documented in the subject's medical record and in the eCRF.
- The EOT visit should be performed (see Section 6.3).
- Subjects must be followed for safety until the time of the follow-up visit or until study drug–related toxicities resolve, return to baseline, or are deemed irreversible, whichever is longest.

If the subject discontinues study treatment and actively withdraws consent for collection of follow-up data (safety follow-up or disease assessment), then no additional data collection should occur; however, subjects will have the option of withdrawing consent for study treatment but continuing in the follow-up period of the study for safety/efficacy assessments.

5.2.8. Concomitant Medications

All concomitant medications and treatments must be recorded in the eCRF. Any prior medication received up to 30 days before enrollment (Cycle 1 Day 1) will be recorded in the eCRF. Concomitant treatments and/or procedures that are required to manage a subject's medical condition during the study will also be recorded in the eCRF.

5.2.8.1. Restricted Medications

- Chronic use of systemic corticosteroid doses ≤ 10 mg/day prednisone (or equivalent) is permitted but discouraged from the screening visit through the EOT visit or last dose of study drug.
- Short courses of systemic corticosteroid doses > 10 mg/day prednisone (or equivalent) are permitted (eg, for transfusion reaction prophylaxis) but discouraged from the screening visit through the EOT visit or last dose of study drug.
- Chronic acetaminophen use is discouraged; however, if it is required and no alternative therapies are available, acetaminophen less than 2 g per day is permitted.
- Use of weak or moderate inducers or inhibitors of CYP3A4 ([Appendix M](#)) is discouraged, and investigators should seek other options where possible.
- P-glycoprotein substrates with a narrow therapeutic index ([Appendix N](#)) should be used with caution.

CONFIDENTIAL

CONFIDENTIAL

- Hydroxyurea should not be used within 48 hours before and on the day of PD sample collection or during or 72 hours before or after azacitidine administration. Hydroxyurea is prohibited in C-TGC subjects.
- For subjects taking INCB053914 in combination with ruxolitinib only:
 - Aspirin in doses exceeding 125 mg/day is not permitted. Low-dose aspirin (≤ 125 mg/day) is permitted.
 - Caution should be used when administering ibuprofen or other nonsteroidal anti-inflammatory drugs with long elimination half-lives; subjects should be monitored closely for toxicity, especially for myelosuppression and renal and gastrointestinal toxicity.

Additional timed PK testing following the serial timepoints schedule for the respective monotherapy or combination regimen may be required if subjects initiate or require a dose modification of inhibitors or inducers of CYP3A4 or of P-gp substrates during the study.

